6.1.2. Non-insulin Glucose-Lowering Medications

6.1.2.1. Baseline

IS Cohort participants are treated with insulin alone or plus up to four non-insulin glucose-lowering medications.

Non-insulin glucose-lowering medications must be stable (no change of medication or dose) for at least 3 weeks except for TZD which should be stable for 8 weeks prior to baseline visit.

6.1.2.2. Peri-procedural Period

Peri-procedurally, metformin should be held the day prior to endoscopy and resumed post procedure when the patient tolerates oral intake. The dose of sulfonylureas or meglitinides will be reduced by 50% (or discontinued if on the lowest recommended dose) one day before the index procedure to avoid potential hypoglycemic risks. If an episode of documented or symptomatic hypoglycemia is experienced during the peri-procedure or transitional diet period, further reduction of sulfonylurea or meglitinide dose by 50% or discontinuation if on the lowest dose should occur. In the absence of hypoglycemia, sulfonylureas or meglitinides may be resumed to the baseline dose when the patient transitions to soft food (i.e. one week post procedure).

The background SGLT2i should be held three (3) days prior to the index procedure and resumed when the patient transitions to soft food (i.e. one week post procedure).

GLP-1 Receptor agonists and DPP4 may be held in the peri-procedure period if the subject experiences significant nausea and/or vomiting and can be resumed once symptoms resolve at the discretion of the principal investigator.

6.1.2.3. Follow Up Period

During follow-up the baseline non-insulin glucose-lowering medications will be maintained at stable dosing for the duration of the study except as described above.

The background medications may be discontinued only if clinically justified by the PI. Reasons for medication discontinuation may include medication intolerance, drug-related complications, acute renal insufficiency, or worsened chronic renal insufficiency based on repeat eGFR values (eGFR<45 mL/minute/1.73m²), among others as judged by the investigator.

6.2. Rescue Criteria

Participants meeting any of the following criteria after insulin withdrawn should be evaluated for Rescue therapy.

- Fasting glucose > 10 mmol/L, confirmed by repeat measure on two separate days.
- Average daily glucose > 13.3 mmol/L or higher than pre-procedure baseline average by CGM with at least five days of CGM data at any time during follow-up.
- HbA1c >8.0% or improvement <0.5% from baseline if the baseline HbA1c was above 8.0%, after week 12 visit.
- If a non-insulin glucose-lowering medication must be discontinued, and participant's HbA1c is >7.5% 12 weeks after discontinuation of the medication.

Rescue therapy may include re-initiation of insulin and may also include addition of other non-insulin medications.

6.3. Diabetic Ketoacidosis

Patients with diabetes taking SGLT2i medications may develop diabetic ketoacidosis (DKA) including euglycemic DKA.

Participants treated with SGLT2i who present with signs and symptoms consistent with ketoacidosis, including nausea, vomiting, abdominal pain, malaise, and shortness of breath, should be assessed for ketoacidosis, even if blood glucose levels are below 14 mmol/L (250 mg/dL). If ketoacidosis is suspected, discontinuation or temporary interruption of SGLT2i should be considered and the patient should be promptly evaluated and treated.

Pre-disposing factors to ketoacidosis include a low beta-cell function reserve resulting from pancreatic disorders (e.g. type 1 diabetes, history of pancreatitis, or pancreatic surgery), insulin dose reduction, reduced caloric intake, or increased insulin requirements due to infections, illness or surgery and alcohol abuse.

Participants taking SGLT2i should be educated on DKA risks, common symptoms, and instructed to contact study staff immediately if they experience the above symptoms or risk factors.

7. STUDY EVALUATION AND STUDY VISITS

Participants will have the same study evaluations and follow up schedule as in NIS Cohort described in the main study protocol. Points specific to IS Cohort participants are described below.

7.1. Screening Visit

Individuals with T2D requiring basal insulin with or without short/rapid-acting insulin (up to 60 IU/day, and the short- or rapid-acting component $\leq 30\%$ of total daily dose) and an HbA1c between 7.0% - 9.5% will be screened for IS Cohort eligibility. Informed consent must be obtained prior to any study-specific evaluations are performed. A Screening Consent may be used optionally to facilitate the workflow at the study site.

Screening assessments are the same as those in NIS Cohort which are described in the main protocol.

For fasting blood sample collection at the screening, participants will be instructed to have the blood sample collected in the morning after an overnight fasting (>8 hr) and administer 1/3 of their daily insulin dose in the evening preceding the blood sample collection to provide adequate beta-cell stimulation for c-peptide measurement. After the blood collection, participant will administer a third (1/3) of their daily insulin dose. If insulin is given in the morning as a single dose, the morning dose will be held until after blood draw.

7.2. Baseline Visit

Individuals who meet the screening eligibility criteria will be scheduled for baseline visit. The baseline visit will be conducted within 4 weeks from the index procedure. If a screening consent was used at the screening visit, the full study consent must be obtained at this visit. .

Participants who no longer meeting the eligibility criteria at the baseline visit will be considered screen failure and exit the study.

For fasting blood sample collection at the baseline visit, participants will be instructed have the blood sample collected in the morning after an overnight fasting (>8 hr) and to skip their daily insulin dose the evening prior to blood collection. After the blood collection, participant will administer a third (1/3) of their daily insulin dose.

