7.7 Laboratory Assessments

Local laboratories with appropriate accreditation will be used for all laboratory tests. Specific tests required at each visit are outlined in SoA (**Appendix 2**).

Fasting blood samples will be obtained at the screening and baseline visits, and at Week 1, 4, 12, 24, 36, and 48.

At these fasting visits, participants will not take any food or liquid within the last 8 hours prior to blood sampling, however water is allowed up until 2 hours prior to blood sampling. Participants can take their regular morning medications but should be advised not to take any of their diabetes medications on the morning of their study visit. Participants should bring their diabetes medications to their study visits and take them after blood sampling.

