6.1.1.3. Allowed pre-mixed insulin includes

- NovoMix® 30 (30% rapid, 70% intermediate Protaphane)
- Humalog® Mix 25 (25% rapid, 75% intermediate Humulin NPH)
- Ryzodeg 70:30 (70% long acting Degludec, 30% rapid Aspart)
- Mixtard® 30/70 (30% short, 70% intermediate Protaphane)
- Humulin® 30/70 (30% short, 70% intermediate Humulin NPH).

For the index procedure, participants will be instructed to fast overnight. A general recommendation is to administer 50% of their typical insulin dose at their usual time typically the preceding evening or the morning of the procedure day. However, the investigator should individualize insulin management for each subject particularly if S/RA is a component of their insulin regime.

- Following the procedure, participant's baseline insulin dose will be reduced to avoid hypoglycemia in the setting of a reduced caloric intake post procedure. Subsequently the insulin dose will be titrated to achieve a fasting glucose target of 5.0 – 7.2 mmol/L. Specifically, the following algorithm will be instituted.
- Continue insulin at 50% of the baseline dose on day 1 post procedure.
- Increase insulin dose by 2 units or 10% (as per recommendation of the treating investigator or provider) if fasting glucose is above the target of 7.2 mmol/L over 3 consecutive days.
- Alternatively, reduce insulin dose by 2 units or 10% (as per recommendation of the treating investigator or provider) for a single morning blood glucose or CGM reading less 5.0 mmol/>, or any episode of symptomatic hypoglycemia.
- If daily insulin dose is reduced to 10 units or 0.1 units/kg and fasting glucose is within the target range, insulin may be discontinued with close follow up of glycemia through CGM.
- If insulin is not completely withdrawn by 24 weeks, the background therapy may be intensified to further decrease or eliminate reliance on exogenous insulin. Intensification of background therapy may include addition of a GLP-1a, or an SGLT2i if the participant is already taking or has demonstrated an intolerance to GLP-1a. The insulin titration following intensification of background glycemic therapy should follow the same algorithm as described above.

The above algorithm is provided as a guideline. Investigator should apply clinical judgement to individualize therapy including insulin dosing and background glycemic medications.

Participants in the IS cohort should be instructed to use CGM to monitor his/her glucose levels throughout the duration of the study.

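### Insulin cohort: evening insulin is skipped before the baseline fasting sample but not before follow-up samples, so FPG change tilts toward improvement in participants still on evening insulin

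*Protocol*

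**What the plan says.** **Baseline.** Protocol Appendix 4, section 7.2 instructs participants "to skip their daily insulin dose the evening prior to blood collection" and to take one third of the daily dose after the draw.

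**Follow-up.** Appendix 4, section 7 sets no sampling rule of its own after baseline: "Participants will have the same study evaluations and follow up schedule as in NIS Cohort described in the main study protocol". It adds insulin-cohort points only for screening (7.1) and baseline (7.2). Main protocol section 7.7 then governs, and there participants "should be advised not to take any of their diabetes medications on the morning of their study visit". It does not mention the evening before. Neither the mixed meal test section (7.8) nor the Schedule of Activities and its notes (Appendix 2) adds an evening rule.

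**Insulin after the procedure.** Appendix 4, section 6.1.1.3 says: "Continue insulin at 50% of the baseline dose on day 1 post procedure". It then says: "Subsequently the insulin dose will be titrated to achieve a fasting glucose target of" 5.0 to 7.2 mmol/L. The dose goes up "if fasting glucose is above the target of 7.2 mmol/L over 3 consecutive days" and down "for a single morning blood glucose or CGM reading less 5.0" mmol/L. Insulin may be stopped once the dose is down to 10 units or 0.1 units/kg with fasting glucose in target.

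**Who doses in the evening.** Section 6.1.1.1 allows detemir and NPH twice daily and fixes no time of day for once-daily glargine or degludec. For the procedure itself, section 6.1.1.3 recommends that participants "administer 50% of their typical insulin dose at their usual time typically the preceding evening or the morning of the procedure day", so evening dosing is expected.

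**Endpoints.** Appendix 4, Table 1 lists change from baseline by visit in FPG and HOMA-IR. Appendix 4, section 11 has efficacy analysed by cohort.

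**The concern.** A change from baseline is interpretable only if both measurements are taken under the same conditions. Here the baseline sample follows a night without evening insulin, and the follow-up sample follows a night with whatever evening dose is still prescribed. Take a participant whose regimen and on-insulin fasting glucose never change: baseline FPG is raised by the skipped dose, follow-up FPG is not, and the record shows a fall. The study is single-arm, so no control group offsets this. HOMA-IR combines fasting glucose with fasting insulin, and an evening dose can move both, so its change is distorted in a direction the documents do not settle.

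The omission does not look like shorthand for a general rule. The addendum sets evening insulin visit by visit (one third of the daily dose before the screening draw, none before the baseline draw) and then stops.

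**Working it through.** The plan states no FPG effect, standard deviation or power for this cohort, so there is no figure to reproduce. The check sets the rules side by side and then asks what scale is possible.

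**Step 1. Insulin on board at each fasting glycemic sample, following the text**

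| Participant | Baseline | Weeks 4, 12, 24, 36, 48 | Matched? |
|---|---|---|---|
| Evening or twice-daily insulin, still taken | evening dose skipped, morning held | evening dose taken, morning held | No |
| Evening insulin, since stopped | evening dose skipped | none | Yes |
| Morning-only insulin | held until after draw | held until after draw | Yes |

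Main protocol 7.7 also lists a Week 1 fasting sample, but the Schedule of Activities has no FPG or HOMA-IR at that visit. The exposure begins at Week 4.

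**Step 2. Direction and form**

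Let d be the FPG rise caused by skipping the baseline evening dose, and r the follow-up evening dose as a fraction of the baseline one. Assume the effect is proportional to dose. Compared with two samples both drawn without the evening dose, the recorded change in an affected participant is shifted by −(r × d). With s the share still on insulin and e the share of those dosing in the evening:

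shift in cohort mean FPG change = −(s × e × r × d)

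The sign is never positive. A reduced follow-up dose shrinks the shift and does not reverse it.

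**Step 3. Inputs**

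- Cohort size: 20, up to 30 (Appendix 4, section 4).
- r = 0.5 at the day 1 restart; r = 1 if back at the full baseline dose.
- s is not given for this device. As an illustration only, Appendix 4, section 1 cites an earlier study in 16 patients with 69% off insulin and at HbA1c target at 6 months: 0.69 × 16 = 11.04, so 11 of 16, leaving 5/16 = 0.31. That is 0.31 × 20 = 6.2 or 0.31 × 30 = 9.3 participants. For that study 0.31 is an upper bound, since some may have been off insulin but above target. It used another technique and, by the title in the reference list, a GLP-1 receptor agonist, so s may be higher here.
- d is not given. Assumed range: 0.5 to 3 mmol/L.

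**Step 4. Results**

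| s | e | r | s × e × r | Shift in mean FPG change if d = 0.5 to 3 mmol/L (assumed) |
|---|---|---|---|---|
| any | 0 | any | 0 | 0 |
| 0.31 | 1 | 0.5 | 0.155 | −0.08 to −0.47 |
| 0.31 | 1 | 1 | 0.31 | −0.16 to −0.93 |
| 1 | 1 | 0.5 | 0.50 | −0.25 to −1.5 |
| 1 | 1 | 1 | 1.00 | −0.5 to −3.0 |

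The last two rows are limits, not forecasts. Early visits may still lie well above s = 0.31: at the maximum permitted 60 IU/day the restart dose is 0.5 × 60 = 30 IU, against a stopping threshold of 10 units, and the dose moves in steps of 2 units or 10%.

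**The case against.** - **The off-insulin baseline is deliberate.** Appendix 4, section 3 frames exploratory efficacy as glycemic control without exogenous insulin, and the skipped-dose baseline suits that aim. This stands: it confines the mismatch to those who have not stopped insulin. It does not repair it for them.
- **Silence is not an instruction.** No text tells participants to take evening insulin before follow-up draws, and section 6.1.1.3 lets investigators individualise dosing. But the prescribed evening dose continues unless someone stops it, and sites that choose differently would make the samples less comparable still, with no required per-sample record.
- **FPG is already confounded.** Insulin is titrated to a fasting target, and a GLP-1 agonist or SGLT2 inhibitor may be added after Week 24. True, and matching one evening's dose would not isolate a device effect. The measurement mismatch is a separate artefact on top.
- **Little rests on it.** Efficacy is exploratory and summaries are descriptive. The SAP describes a 20-patient study of non-insulin-treated patients and holds no FPG model for this cohort. This stands and limits the weight of the point.

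A reader might infer that FPG change is biased in every evening or twice-daily insulin user, or across the whole cohort. The documents do not support that: evening users who have stopped, and morning-only dosers, are matched. Nor do they support attaching a mmol/L figure, since d is absent and s is borrowed from a different treatment.

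**Conclusion.** The mismatch is real for participants still on evening or twice-daily insulin at a follow-up visit. In them, a site following the text will record an FPG change biased toward improvement and a HOMA-IR change that is not comparable with baseline. For twice-daily users this reads the baseline instruction as covering the evening part of a split dose, which is an inference.

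The size cannot be derived. The multiplier on d runs from 0 to 1.0, and the mmol/L values above rest on an assumed d and on proportionality to dose. A reader might go on to doubt the HbA1c results or the 12-week safety endpoint; neither depends materially on one evening's dose. This is a worthwhile, inexpensive clarification of exploratory endpoints, not a flaw in the study's main conclusion.

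**What to change.** 1. Record the dose and time of the last insulin with every baseline and follow-up fasting sample, including mixed meal test mornings, when that test replaces the separate FPG sample (Schedule of Activities, note 6). Baseline needs it too: if screening and baseline are combined (main protocol 7.12.2), the addendum's two evening rules conflict.
2. Report FPG and HOMA-IR change descriptively by insulin status and evening-dose status at the visit, including for samples already collected where the status is known. Treat the off-insulin stratum as the like-for-like comparison, noting that it is selected: stopping requires fasting glucose in target.
3. For those still on evening insulin, show fasting-hour CGM glucose under usual dosing at baseline and at follow-up, alongside the insulin dose at each time. Exclude the skipped-dose night and the half-dose night before the procedure. The data should exist: this cohort wears CGM at baseline and throughout follow-up (main protocol 7.10; Schedule of Activities, note 7; Appendix 4, 6.1.1.3).
4. Make skipping the evening dose at follow-up visits optional at most. Doing so routinely would mean up to five skipped doses per participant, and Appendix 4, section 6.3 names insulin dose reduction as a predisposing factor for ketoacidosis, including the euglycemic form in SGLT2 inhibitor users. Exempting those users would leave their mismatch in place, so this should not be the main remedy.

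Cost: one eCRF field, a little more analysis, and small strata in a cohort of 20 to 30. Items 1 to 3 withhold no insulin.

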8. STUDY AND PARTICIPANT DISCONTINUATION

Study and participation discontinuation is described in the main protocol.

9. SAFETY ASSESSMENT

Safety assessment is described in the main protocol.

10. MEDICAL SAFETY MONITORING

Medical safety monitoring is described in the main protocol.

11. STATISTICAL DESIGN AND ANALYSIS

Statistical analysis will be performed in accordance with the main protocol. The data on safety and procedural feasibility will be analyzed for each cohort and overall. The data on efficacy endpoints will be analyzed by treatment cohort.

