--	---

	
measurement that is confirmed by a second measurement (not on the same day) since screening visit
 
42. Mean of 3 separate blood pressure measurements >180 mmHg (systolic) or >100 mmHg (diastolic)
 
43. Women of child-bearing potential with a positive urine pregnancy test at baseline visit
 
44. LA Grade C or greater esophagitis on endoscopy
 
45. Abnormalities of the GI tract preventing endoscopic access to the duodenum
 
46. Anatomic abnormalities in the duodenum that would preclude the completion of the treatment procedure, including tortuous anatomy
 
47. Endoscopic observation of upper gastrointestinal abnormality such as ulcers, duodenal polyps in the area to be treated, varices, strictures, congenital or intestinal telangiectasia
 
48. Any other anatomical or endoscopic abnormalities/characteristics that, in the opinion of the investigator, would preclude safe use of the investigational device or procedure

Assessment Schedule	
 Visits: Screening, Baseline, Index Procedure, Week 1, Week 2, Week 4, and every 4 weeks thereafter Pancreatic enzyme: Baseline, Week 1 Glycemic parameters: Baseline, Week 4, 12, 24, 36, 48 Metabolic panel: Screen, Baseline, Week 1, 12, 24, 48 Fasting lipid panel: Baseline, Week 24, 48 Continuous blood glucose monitoring (CGM): Baseline, Day 1-Week 4, Week 12, 24, 36, and 48 Endoscopic follow up: Week 2-5 Diabetes review and medication titration will be performed by the treating physician at all visits (see Schedule of Activities)

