6.8 Participant Education and Lifestyle Counseling

6.8.1 Hypoglycemia

At the onset of the study, participants should be educated on the potential for development of hypoglycemia, the symptoms and signs of hypoglycemia, instruction in the use of continuous blood glucose monitoring to detect hypoglycemia, and instruction on treating hypoglycemia. Symptoms suggestive of hypoglycemia include lightheadedness, tremor, shaking, sweating, tingling, blurred vision, difficulty concentrating, and confusion. With marked hypoglycemia, patients may develop altered consciousness, coma, or seizures.

Participants will use CGM for at least 5 days at baseline and for 28 days after the procedure, followed by a 7-day monitoring at each of the 3-, 6-, 9-, and 12-month follow up visits. Participants should be instructed to promptly contact site staff for any documented or suspected hypoglycemia during the study.

The definition of hypoglycemic episodes can be found in **Appendix A**. Study participants or study staff may identify these episodes.

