APPENDIX 1. DEFINITIONS

The Los Angeles Classification of esophagitis¹¹

- Grade A: One (or more) mucosal break no longer than 5 mm that does not extend between the tops of two mucosal folds
- Grade B: One (or more) mucosal break more than 5 mm long that does not extend between the tops of two mucosal folds
- Grade C: One (or more) mucosal break that is continuous between the tops of two or more mucosal folds but which involve less than 75% of the circumference
- Grade D: One (or more) mucosal break which involves at least 75% of the esophageal circumference

Hypoglycemia (ADA 2020)

- Level 1 hypoglycemia is a glucose concentration 54–70 mg/dL (3.0–3.9 mmol/L).
- Level 2 hypoglycemia is a blood glucose concentration <54 mg/dL (3.0 mmol/L), which is typically the threshold for neuroglycopenic symptoms.
- Level 3 hypoglycemia is a clinical event characterized by altered mental and/or physical functioning that requires assistance from another person for recovery

Severe hypoglycemia: Level 3 hypoglycemia per ADA 2020 definition.

Documented symptomatic hypoglycemia: An episode during which typical symptoms of hypoglycemia are accompanied by a measured plasma glucose concentration ≤ 3.9 mmol/L (70 mg/dL).

Probable symptomatic hypoglycemia: An episode during which symptoms of hypoglycemia are not accompanied by a plasma glucose determination but that was presumably caused by a plasma glucose concentration ≤ 3.9 mmol/L (70 mg/dL).

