Serum Iron, transferrin, saturation, ferritin, serum folate, Vitamin D, Vitamin B12			X								X						X	X	
CBC with differential	X	X		X		X		X			X			X			X	X	
Serum Glutamic acid decarboxylase antibody (Anti-GAD)	X																		
H. Pylori test ^[3]	X	X																	
Pregnancy test ^[4]	X	X																	
EKG		X																	
ENDOSCOPIES																			
DMR procedure			X																
Endoscopic follow up							X ^[5]												
SAFETY																			
Hypoglycaemic episodes	X	X	X	X	X	X	X	X	X	X	X	X	X	X	X	X	X	X	X
CGM ^[7]		X	X	X	X	X		X			X			X			X	X	X
Adverse events	X	X	X	X	X	X	X	X	X	X	X	X	X	X	X	X	X	X	X

^[1] Screening and baseline visits may be combined if screening visits or tests falls within baseline visit window.

^[2] Metabolic panel includes albumin, total protein, , ALP (alkaline phosphatase), ALT (alanine transaminase), AST (aspartate aminotransferase), bilirubin, urea, creatinine, eGFR.

^[3] breath or stool test

^[4] For women with child-bearing potential.

^[5] Endoscopic follow-up target window is between Week 2-5.

^[6] Only when MMTT is not performed.^[7] CGM will be used for the duration of the follow up in insulin cohort.

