For Adverse Event reporting, which includes primary and secondary variables, the primary analysis will be based on Patient counts (e.g., the number and percentage of Patients with events among the total number of Patients). The data will be presented in the format of p% (x/N) [e], with p and x being the percentage and number of Patients with events, respectively, N being the sample size of the analysis population, and e being the total number of events occurred in the x Patients. Asymptotic confidence limits will be presented based on the normal approximation to the binomial distribution for differences in proportions. Exact confidence intervals will be used for all other presentations.

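### Hypoglycemia summaries take no account of CGM time, so CGM-detected Level 1 and 2 figures are not comparable between the non-insulin and insulin cohorts and should not be pooled as they stand

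*Protocol*

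**What the plan says.** **Analysis rule.** Protocol Appendix 4 section 11 says "The data on safety and procedural feasibility will be analyzed for each cohort and overall"; only efficacy is kept to separate cohorts. It otherwise defers to the main protocol. Section 11.4.2 there gives, for each type of event, the number of events and the number and percent of participants. It has no exposure or wear-time denominator.

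**Hypoglycemia as safety data.** Hypoglycemic episodes are a row under the safety heading of the Schedule of Activities (Appendix 2), at every visit. Section 10 sends hypoglycemic events to the medical monitor for adjudication.

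**Definition.** Appendix 1 defines Levels 1 and 2 by a glucose value, with no symptom required: "Level 2 hypoglycemia is a blood glucose concentration <54 mg/dL (3.0 mmol/L"). Level 3 is a clinical event in which the participant needs another person's help.

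**CGM wear, NIS cohort.** Section 6.8.1 prescribes CGM "for 28 days after the procedure, followed by a 7-day monitoring at each of the 3-, 6-, 9-, and 12-month follow up visits". The Protocol Summary and section 7.10 give the same timepoints.

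**CGM wear, IS cohort.** Footnote 7 of Appendix 2 says "CGM will be used for the duration of the follow up in insulin cohort". Appendix 4 section 6.1.1.3 says "Participants in the IS cohort should be instructed to use CGM to monitor his/her glucose levels throughout the duration of the study".

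**The concern.** An asymptomatic Level 1 or Level 2 episode is found mainly while a sensor is on. If one cohort wears the sensor six times as long, its count of such episodes, and its percentage of participants with at least one, will be higher even when the true rates are equal. Event counts are affected in the same way as participant counts.

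Three things are at stake:

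- The NIS and IS results will be read side by side, although they were observed for different lengths of time.
- The overall figure averages two quantities that do not measure the same thing, weighted by however many participants each cohort happens to enrol.
- Insulin carries its own hypoglycemia risk. A reader of the planned tables could not tell how much of a difference comes from treatment and how much from monitoring.

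**Working it through.** The plan states no hypoglycemia rate, so it has no figure of its own to reproduce. The exposure figures follow from the schedules; the rest is an illustration on stated assumptions.

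**Step 1: CGM days after the procedure**

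- NIS (section 6.8.1): 28 + 4 × 7 = 56 days. The baseline wear of at least 5 days precedes the safety window and is left out.
- IS (Appendix 2 footnote 7; 48-week follow-up): 48 × 7 = 336 days at full wear.
- Ratio: 336 / 56 = 6.0. NIS is covered for 56 / 336 = 16.7% of follow-up.

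If only CGM finds episodes and true rates are equal, expected event counts per participant also differ 6-fold, whatever the rate.

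**Step 2: participants with at least one detected episode, CGM-only detection**

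Formula: P = 1 − exp(−r × t / 365.25), where r is episodes per patient-year (assumed, equal in both cohorts) and t is 56 or 336 days.

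| r (assumed) | NIS | IS | IS/NIS |
|---|---|---|---|
| 0.25 | 3.8% | 20.5% | 5.46 |
| 0.5 | 7.4% | 36.9% | 5.00 |
| 1 | 14.2% | 60.1% | 4.23 |
| 2 | 26.4% | 84.1% | 3.19 |
| 5 | 53.5% | 99.0% | 1.85 |
| 10 | 78.4% | 100.0% | 1.28 |

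**Step 3: allow for episodes found off CGM**

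Let a share s of the NIS episodes outside CGM wear be found through symptoms or self-monitoring. The effective NIS time is then t = 56 + s × (336 − 56) = 56 + 280s. At r = 1, with IS at 60.1%:

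| s (assumed) | Effective t (days) | NIS | IS/NIS |
|---|---|---|---|
| 0 | 56 | 14.2% | 4.23 |
| 25% | 126 | 29.2% | 2.06 |
| 50% | 196 | 41.5% | 1.448 |
| 100% | 336 | 60.1% | 1.00 |

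**Step 4: the overall figure**

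Pooled percentage = (n_NIS × 14.2% + n_IS × 60.1%) / (n_NIS + n_IS), at r = 1 with CGM-only detection. The cohort sizes lie within the planned ranges (NIS 20 up to 60, IS 20 up to 30).

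- 20 NIS + 20 IS: 37.2%
- 60 NIS + 20 IS: 25.7%
- 60 NIS + 30 IS: 29.5%

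The true rate is the same in all three; only the mix changes. At 60 + 30, the IS cohort supplies 30 / 90 = 33% of participants but 30 × 336 / (60 × 56 + 30 × 336) = 75% of CGM days.

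**Step 5: effect of the correction**

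Per CGM-day worn, equal and constant true rates give a ratio of 1.0. Restricted to the shared windows, both cohorts have t = 56, so the ratio is again 1.0 under the Step 2 assumptions.

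**The case against.** The strongest case on the other side has five parts.

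- **Hypoglycemia is not named, and no cohort comparison is planned.** Appendix 4 section 11 speaks of safety data in general and keeps per-cohort results; section 11.4.2 tests no hypothesis; hypoglycemia is not a listed endpoint. This stands as a limit: coverage is by category and the use is descriptive. It does not remove the problem, because the per-cohort figures are themselves the non-comparable ones.
- **The SAP does not govern this display.** A reader might take the SAP's statement that "the primary analysis will be based on Patient counts" as the rule for showing NIS against IS. The documents do not support that. The SAP is written for REGENT-1-US, Doc. No. 346, with 20 patients on non-insulin agents; despite stray references to an IS population, it defines no insulin cohort. Its format also adds the number of events, and it plans CGM time in range. The point rests on Appendix 4 section 11 and main protocol section 11.4.2 alone.
- **Sensors are not the only route to detection.** Episodes are asked about at every visit, participants or staff may identify them, and willingness to self-monitor glucose is an inclusion criterion for both cohorts. This stands, and Step 3 shows it drives the size of the effect. The 4.2 ratio also supposes that every sensor episode is recorded, although only severe episodes are expressly sent to the adverse event form.
- **IS wear is an instruction.** The 336 days are a maximum. This stands, and argues for counting days actually worn.
- **Detection is not the only explanation.** A reader might infer that any excess in the IS cohort would be a monitoring artefact. The documents do not support that either: Appendix 4 section 1 itself associates insulin with hypoglycemia, and Level 3 and symptomatic episodes need no sensor.

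**Conclusion.** The point holds for CGM-detected Level 1 and Level 2 episodes. The plan summarises safety data by cohort and overall without allowing for CGM time, while scheduled post-procedure wear is about 56 days in one cohort and up to 336 in the other. Those figures are not comparable between cohorts, and the overall figure has no stable meaning.

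The 6-fold wear difference comes from the documents and assumes full IS wear. How far it distorts participant percentages depends on two quantities the documents do not give. At 1 episode per patient-year the ratio runs from 4.2 (CGM-only detection) down to 1.0 (everything found another way). With CGM-only detection it runs from 5.5 at 0.25 per patient-year to 1.3 at 10. These are illustrations, not predictions.

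Detection time and the true effect of insulin are confounded; the planned display cannot separate them, and neither can be named as the sole cause. Level 3 counts do not depend on CGM, and the primary endpoint (device- or procedure-related serious adverse events at 12 weeks) is little affected. This is a reporting correction to a descriptive safety summary, worth making because it is cheap.

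**What to change.** In Protocol Appendix 4 section 11, add that:

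1. CGM-detected Level 1 and Level 2 hypoglycemia is reported by cohort as events per 100 CGM-days actually worn, with wear derived from the CGM data, and as percent of CGM time below 70 and below 54 mg/dL.
2. Any side-by-side or overall summary of these episodes uses only the windows both cohorts share: Day 1 to Week 4, and 7 days at each of Weeks 12, 24, 36 and 48. A per-day rate alone is not enough if risk changes over follow-up: the first 28 days are 28 / 56 = 50% of NIS wear but 28 / 336 = 8.3% of IS wear.
3. Participant counts are kept for Level 3 and symptomatic events.

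The cost is a few lines of text and a little extra programming. No new visits or measurements are needed: section 12.3.1 lists CGM data as source data, section 13.2 provides for their integration into the analysis, and exclusion criterion 40 already uses percent of CGM time below 54 mg/dL. Wear dates are not a listed data item, hence their derivation from the CGM data. IS data outside the shared windows drop out of side-by-side and overall summaries only and stay in the IS cohort's own results.
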